7.1.2 Procedures for Assigning Subjects to Intervention Groups

Eligible subjects who meet all inclusion criteria and do not meet any exclusion criteria will be randomised. Randomisation will be carried out using standard procedures. Randomisation numbers will not be reused for any reason.

7.2. Procedures by Study Phase

The assessments and procedures to be completed during each of the study phases are described in the sections that follow and in the Schedule of Events and Procedures provided in **Appendix A**. Detailed descriptions of the study assessments and measurements are provided in 8. Screening Phase (Visit 0)

The following will be performed during the Screening Visit including:

- review inclusion/exclusion criteria for eligibility
- collect demographics
- collect medical, social, sexual, and medication history
- perform diagnostic screening for HSDD
- perform vital signs assessment (systolic and diastolic BP, heart rate, temperature)
- perform comprehensive physical examination
- perform 12-lead ECG
- collect blood and urine for clinical laboratory tests including:
 - hematology
 - serum chemistry
 - urinalysis
 - FSH, LH, oestradiol, progesterone, prolactin, dehydroepiandrosterone sulphate (DHEAS), androstenedione & testosterone

- urine pregnancy test
- DNA analysis (if patient consents) to assess for novel genes implicated in the aetiology of HSDD
- have subject complete questionnaires/assessments such as:
 - PHQ-9
 - BSS
 - Decreased Sexual Desire Screener (DSDS) (Clayton et al., 2009)
 - FSFI
 - FSDS-DAO
 - MMAS
- schedule study visits for participants who are eligible and available for the duration of the study
- advise participants to consume a normal breakfast on day of study and abstain from sexual activity, alcohol, caffeine and tobacco from midnight before their study visits
- MRI safety questionnaire

7.2.1 Intervention Phase (Visits 1 and 2)

Visit 1

Visit 1 will occur after Screening (Visit 0), on **day 1-7** of the menstrual cycle. Subjects will be randomised and the following procedures will be performed:

- On arrival
 - review and confirm study eligibility
 - perform vital signs assessment (systolic and diastolic BP, heart rate, temperature)
 - perform symptom-driven physical examination
 - collect blood and urine for clinical laboratory tests (haematology, serum chemistry, urinalysis)
 - perform urine pregnancy test
 - review concomitant medications
 - MRI safety questionnaire
- Prior to intervention
 - remove intervention autoinjector from assigned study kit; warm to room temperature
 - collect arousal/psychometric data using behavioral potentiometer (including the Visual Analogue Scale (VAS), the State-Trait Anxiety Inventory (STAI Y1 and

Y2), the Sexual Arousal and Desire Inventory (SADI) and the Positive and Negative Affect Schedule (PANAS) at the end of scanning component of session (see Appendices E to I).

- Post-intervention assessments:
 - administer intervention based on randomisation assignment
 - collect blood at time-points: -15, 0 (SC injection), 15, 45, 60, 75, 90, 120, 150, 180, 210, 240, 270, 300 (14 timepoints total). A maximum of 12ml will be taken at each time-point. The total volume of blood collected over both study visits will not exceed 340ml.
 - During SS1:
 - perform fMRI in accordance with Imaging Manual instructions (including functional MRI scan (commencing t=45mins) and anatomical MRI scan)
 - Exposure to visual erotic stimuli as well as other tasks designed to elicit brain responses related to emotional, sensory, or cognitive functions.
 - collect psychometric data using behavioral potentiometer alongside session (arousal handheld device in scanner and psychometric/behavioral potentiometer questionnaires including the Visual Analogue Scale (VAS), the State-Trait Anxiety Inventory (STAI Y2), the Sexual Arousal and Desire Inventory (SADI) and the Positive and Negative Affect Schedule (PANAS) at the end of scanning component of session (see Appendices E to I).
 - During SS2:
 - perform fMRI (and anatomical scan) in accordance with Imaging Manual instructions (commencing t=240mins)
 - Exposure to stimuli as per SS1.
 - collect psychometric data using behavioral potentiometer alongside session (arousal handheld device in scanner and psychometric/behavioral potentiometer questionnaires including the Visual Analogue Scale (VAS), the State-Trait Anxiety Inventory (STAI Y2), the Sexual Arousal and Desire Inventory (SADI), the Positive and Negative Affect Schedule (PANAS) and the D2 Test of Attention at the end of scanning component of session (see Appendices E to I).

Visit 2

This will occur on **day 1-7** of a subsequent menstrual cycle, to allow for the study to be carried out in the same part of the menstrual cycle on each visit.

The following procedures will be performed:

- On arrival
 - As described for Visit 1
- Prior to intervention
 - As described for Visit 1

- Post-intervention assessments
 - As described for Visit 1

Follow-up

Participants will be sent a short questionnaire 24 hours after the study to assess the perceived duration of effect of BMT (see Appendix J).

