Appendix A: STUDY FLOWCHART

Variables	Screening (Visit 0)	Intervention phase (Visit 1)	Intervention Phase (Visit 2)
Informed Consent Form (ICF)	X		
Review inclusion/exclusion criteria	X	X	X
Demographics	X		
Medical, social and sexual history	X		
Review medications	X	X	X
Perform diagnostic screening for HSDD	X		
Perform baseline screening questionnaires: PHQ-9, BSS, FSFI, FSDS-DAO, MMAS	X		
Vital signs	X	X	X
12-lead ECG	X		
Urine pregnancy test	X	X	X
Physical exam	X	X	X
Clinical laboratory tests	X	X	X
Randomisation		X	
Continued eligibility assessment		X	X
Administer intervention BMT/placebo		X	X
fMRI & behavioral potentiometer (including handheld device and questionnaires such as VAS, STAI Y1 and Y2, SADI, PANAS, D2 Test of Attention)		X	X
Review adverse events		X	X

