APPENDIX E: Visual Analogue Scale

Please place a vertical mark along the line according to how you are feeling

Example:

How hungry do you feel right now?

NOT AT ALL  EXTREMELY

How sick (or nauseous) do you feel right now?

NOT AT ALL  EXTREMELY

How pleasant would it be to eat right now?

NOT AT ALL  EXTREMELY

How much do you think you could eat right now?

NOTHING  A LARGE AMOUNT

How full do you feel right now?

NOT AT ALL  EXTREMELY

How sleepy do you feel right now?

NOT AT ALL  EXTREMELY

APPENDIX F: State-Trait Anxiety Inventory Y-1 and Y-2**SELF-EVALUATION QUESTIONNAIRESTAI Form Y-1****Please provide the following information:**

Name _____ Date _____ S _____

Age _____ Gender (Circle) M F T _____

DIRECTIONS:

A number of statements which people have used to describe themselves are given below. Read each statement and then circle the appropriate number to the right of the statement to indicate how you feel *right now*, that is, *at this moment*. There are no right or wrong answers. Do not spend too much time on any one statement but give the answer which seems to describe your present feelings best.

1. I feel calm.....	1	2	3	4
2. I feel secure	1	2	3	4
3. I am tense	1	2	3	4
4. I feel strained	1	2	3	4
5. I feel at ease	1	2	3	4
6. I feel upset	1	2	3	4
7. I am presently worrying over possible misfortunes	1	2	3	4
8. I feel satisfied	1	2	3	4
9. I feel frightened	1	2	3	4
10. I feel comfortable	1	2	3	4
11. I feel self-confident.....	1	2	3	4
12. I feel nervous	1	2	3	4
13. I am jittery	1	2	3	4
14. I feel indecisive.....	1	2	3	4
15. I am relaxed	1	2	3	4
16. I feel content	1	2	3	4
17. I am worried	1	2	3	4
18. I feel confused.....	1	2	3	4
19. I feel steady.....	1	2	3	4
20. I feel pleasant.....	1	2	3	4

NOT AT ALL
SOMEWHAT
MODERATELY SO
VERY MUCH SO

SELF-EVALUATION QUESTIONNAIRE**STAI Form Y-2**

Name _____ Date _____

DIRECTIONS

A number of statements which people have used to describe themselves are given below. Read each statement and then circle the appropriate number to the right of the statement to indicate how you *generally* feel. There are no right or wrong answers. Do not spend too much time on any one statement but give the answer which seems to describe how you generally feel.

21. I feel pleasant.....	1	2	3	4
22. I feel nervous and restless	1	2	3	4
23. I feel satisfied with myself.....	1	2	3	4
24. I wish I could be as happy as others seem to be	1	2	3	4
25. I feel like a failure	1	2	3	4
26. I feel rested	1	2	3	4

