APPENDIX G: The Sexual Arousal and Desire Inventory (SADI)

Sexual Arousal is defined as the **physiological responses that accompany or follow sexual desire**. For example, when you feel sexually aroused, your heart might beat faster or your palms may get sweaty. Men may experience penile erection, and women may feel a moistness of the vagina. Sexual Arousal involves the more physiological aspects of wanting sex. **Sexual desire is defined as an energizing force that motivates a person to seek out or initiate sexual contact and behaviour**. You can think of it as a hunger or a sexual 'drive' that leads you to seek out sexual contact. Sexual desire involves the more psychological aspects of wanting sex.

Keep in mind the definitions of sexual arousal and sexual desire. Following is a list of words that might **describe how you feel currently**. Different people experience sexual arousal and desire in distinct, individual ways. There is no 'right' or 'wrong' answer. Please indicate to what extent each word describes how you feel **RIGHT NOW**, by placing the number that describes the feeling most accurately.

0 does not describe it at all	1	2	3 describes it moderately well	4	5 describes it perfectly
Anticipatory_____			Frustrated_____		
Tingly all over_____			Lustful_____		
Restrained_____			Entranced_____		
Anxious_____			Aversion_____		
Driven_____			Hot_____		
Frigid_____			Tempted_____		
Sensitive to touch_____			Passionate_____		
Sluggish_____			Fantasize about sex_____		
Urge to satisfy and/or be satisfied_____			Repressed_____		
Enthusiastic_____			Disturbed_____		
Unhappy_____			Flushed_____		
Wet (women only)_____			Impatient_____		
Hard (men only)_____			Sensual_____		
Resistant_____			Breathe faster/pant_____		
Warm all over_____			Displeasure_____		
Excited_____			Stimulated_____		
Tingling in genital area_____			Tingling sensation in gut_____		
Uninterested_____			I forget about everything else_____		
Pleasure_____			Repulsion_____		
Heart beats faster_____			Sexy_____		
Happy_____			Quivering sensations_____		
Angry_____			Insensible_____		
Attractive_____			Seductive_____		
Powerful_____			Genitals reddish_____		
Naughty_____			Unattractive_____		
Alluring_____			Good_____		
Lethargic_____			Throbs in genital area_____		
Horny_____					

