APPENDIX H: The Positive and Negative Affect Schedule (PANAS)

PANAS Questionnaire

This scale consists of a number of words that describe different feelings and emotions. Read each item and then list the number from the scale below next to each word. Indicate to what extent you feel this way right now, that is, at the present moment *OR* indicate the extent you have felt this way over the past week (circle the instructions you followed when taking this measure)

1	2	3	4	5
Very Slightly or Not at All	A Little	Moderately	Quite a Bit	Extremely

_____ 1. Interested	_____ 11. Irritable
_____ 2. Distressed	_____ 12. Alert
_____ 3. Excited	_____ 13. Ashamed
_____ 4. Upset	_____ 14. Inspired
_____ 5. Strong	_____ 15. Nervous
_____ 6. Guilty	_____ 16. Determined
_____ 7. Scared	_____ 17. Attentive
_____ 8. Hostile	_____ 18. Jittery
_____ 9. Enthusiastic	_____ 19. Active
_____ 10. Proud	_____ 20. Afraid

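### After dosing, Section 7.2.1 lists only the trait anxiety form (STAI Y2) and the PANAS time frame is left open, so acute anxiety and mood effects are not reliably measured

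*Combined protocol and SAP*

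**What the plan says.** Section 7.2.1 gives questionnaire lists for three points in each intervention visit, and Visit 2 repeats Visit 1.

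- **Before the intervention:** "collect arousal/psychometric data using behavioral potentiometer (including the Visual Analogue Scale (VAS), the State-Trait Anxiety Inventory (STAI Y1 and", with the trait form, the SADI and the PANAS completing the list. The same bullet places these at the end of the scan.
- **Session 1 (scan starts 45 minutes after injection):** the VAS, then "the State-Trait Anxiety Inventory (STAI Y2), the Sexual Arousal and Desire Inventory (SADI) and the Positive and Negative Affect Schedule (PANAS").
- **Session 2 (scan starts at 240 minutes):** the VAS, then "the State-Trait Anxiety Inventory (STAI Y2), the Sexual Arousal and Desire Inventory (SADI), the Positive and Negative Affect Schedule (PANAS) and the D2 Test". The last of these is an attention test.

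Appendix A has one row for all of this, marked for Visits 1 and 2: "fMRI & behavioral potentiometer (including handheld device and questionnaires such as VAS, STAI Y1 and Y2, SADI, PANAS, D2 Test of Attention"). It is organised by visit and does not separate pre-dose, session 1 and session 2.

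The forms themselves are in the appendices. In Appendix F, Y-1 tells the respondent to "give the answer which seems to describe your present feelings best" and Y-2 to "give the answer which seems to describe how you generally feel". The SADI in Appendix G says "Please indicate to what extent each word describes how you feel", and stresses the present moment. The PANAS in Appendix H offers the present moment or, alternatively, "indicate the extent you have felt this way over the past week (circle the instructions you followed when taking this measure").

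**The concern.** The study gives one injection per visit and measures its effect over the next few hours. A questionnaire repeated in that window should ask about that window. Under Section 7.2.1 as written, the anxiety form repeated after dosing is the one that asks about general disposition, and the state form is named only before the drug is given. The open PANAS frame adds a second problem. Answers could refer to different periods between sessions, between visits or between women, in a crossover that relies on each woman being her own control.

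Section 10.2.3 plans exploratory correlations of brain activation with behavioural data. If a BMT–placebo difference in activation appears, a natural question is whether acute anxiety or mood moved with it. Data not collected during the session cannot be recovered afterwards.

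**Working it through.** The plan states no figure on this point, so the check is mainly a comparison of passages, with a few counts.

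**1. STAI forms named at each point in a visit (Section 7.2.1)**

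| Point | Y1 (state) | Y2 (trait) |
|---|---|---|
| Pre-dose | yes | yes |
| Session 1 | no | yes |
| Session 2 | no | yes |
| Times per visit | 1 | 3 |

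Y1 is named at 0 of 2 post-dose sessions. The omission occurs at both sessions and carries over to Visit 2, so it applies under both BMT and placebo.

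**2. Appendix A against Section 7.2.1.** The Appendix A row is tied to fMRI, which takes place only after dosing, and it names Y1 as well as Y2. Read that way, it implies post-dose Y1. Read simply by visit, the pre-dose Y1 and Y2 satisfy it. The two passages are in tension, not in strict contradiction.

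**3. Other post-dose measures of anxiety or mood**

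- VAS (Appendix E): hunger, nausea, eating, fullness and sleepiness. It has no anxiety or mood item.
- SADI (Appendix G): 28 + 27 = 55 printed items, less 1 for men only, leaves 54 for women. One is named Anxious, and there are other affect words such as Unhappy, Happy, Angry and Frustrated. All refer to the present moment, but they are single items. Y-1 has 20 state items (1 to 20).
- PANAS (Appendix H): includes Nervous, Jittery, Scared, Afraid, Distressed and Upset. It is informative about the acute effect only if answered for the present moment.

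**4. Post-dose share of a past-week PANAS answer**

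One week = 7 × 24 × 60 = 10,080 minutes.

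- Session 1 scan start: 45 / 10,080 = 0.4%
- Session 2 scan start: 240 / 10,080 = 2.4%
- Whole stay of about seven hours (Section 3.1), treated as if all post-dose: 420 / 10,080 = 4.2%

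The questionnaires follow the scan and Section 7.2.1 gives no scan length. The first two figures are therefore lower bounds for each session, and the third is an upper bound.

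**5. Timing of the pre-dose bullet.** It sits under the pre-intervention heading but ties its questionnaires to the end of the scan. The first functional scan starts 45 minutes after injection, so the two instructions cannot both be followed.

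**The case against.** The strongest reply is that the text does not exclude Y1 after dosing. The post-dose lists are introduced as non-exhaustive, Appendix A names Y1 in the fMRI row, and Section 7.2 says procedures are described in both places. A wrong form label or copied text is as plausible as a decision to leave Y1 out, and the misplaced scan clause in the pre-dose bullet points to copying. This stands as a limit on the claim: post-dose Y1 is unclear, not ruled out. It does not remove the problem, because nothing requires Y1 after dosing and completion could vary between sessions or women.

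A second reply is that other data exist. The SADI has several present-moment affect words, and the PANAS used with its first printed option would measure acute negative affect directly. This also stands in part. But the SADI words are single items within an arousal and desire scale, and the PANAS helps only where the present-moment option was used. Circling the option shows which frame was used. It does not make answers with different frames comparable. Nothing in the documents suggests that many women would choose the past week, so the percentages above are conditional on that choice.

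A third reply is that a crossover compares BMT with placebo within session, so a pre-dose Y1 score without a post-dose partner matters less. That is true of the change from baseline. But without Y1 after dosing there is no post-dose state score to compare between interventions either.

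Finally, Section 5.2 names psychometric measures related to sexual arousal, not anxiety or mood, and the only analysis affected is exploratory. This is correct and limits the weight of the point.

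**Conclusion.** The concern holds. If Section 7.2.1 is followed literally, the state anxiety form has no post-dose administration in either visit, and the PANAS may or may not refer to the post-dose period. Acute anxiety and mood could then be examined only weakly alongside a brain-activation difference, from single SADI items and from whichever PANAS answers used the present-moment frame.

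The finding rests on the lists being followed as printed. If sites already give Y1 after dosing and use the present-moment PANAS, the data are sound and only the text needs correcting.

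The primary fMRI endpoint and the arousal endpoints do not depend on these forms, and the sample size in Section 10.3.1 is built on amygdala signal change. The change should be made, but the trial does not stand or fall on it.

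**What to change.** 1. In the session 1 and session 2 bullets of Section 7.2.1, for both visits, replace STAI Y2 with STAI Y1. Keep Y2 before dosing only, as a trait descriptor.
2. Split the Appendix A row by time point: Y1 pre-dose, at session 1 and at session 2; Y2 pre-dose only.
3. Fix the PANAS instruction to the present moment at every administration and remove the alternative from the form.
4. Delete the clause in the pre-intervention bullet that ties its questionnaires to the end of the scan.

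The cost is wording and form selection. Each STAI form has 20 items, so a visit has 20 × (1 + 3) = 80 STAI items as written and 20 × (3 + 1) = 80 after the change. No visit or procedure is added.

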7.3. Subject Discontinuation and Criteria for Withdrawal

7.3.1 Subject Withdrawal

All participants are free to withdraw at any time without giving reasons and without prejudicing future treatment.

8. STUDY ASSESSMENTS AND MEASUREMENTS

8.1. Vital Signs

Systolic and diastolic BP, heart rate, and temperature will be performed at Screening and at Visits 1 and 2 before administration of the intervention and before/after each SS.

8.2. Physical Examination

A comprehensive physical examination including height, weight, BMI, and assessment of all body systems will be performed at Screening. Subsequent physical examinations at Visits 1 and 2 will be symptom-driven based on any AEs, subject complaints about physical state, or subject reported changes in physical state.

8.3. 12-Lead Electrocardiogram

A 12-lead ECG will be performed at Screening and reviewed by a qualified clinician designated by the Principal Investigator to read and interpret the results. Any anomalies will be managed as clinically appropriate and the GP of the patient informed.

8.4. Clinical Laboratory Tests and Visit Assessments

Urine pregnancy tests will be conducted at Screening and at the start of each study visit. Clinical laboratory tests will be performed by a clinical laboratory.

Subjects will be fully informed that the study is evaluating sexual desire brain activity patterns. In conjunction with each fMRI scan, subjective desire will be measured with a behavioral potentiometer.

8.4.1 Safety Assessments

Safety will be monitored with the following assessments: incidence of AEs, vital signs, clinical laboratory tests, and physical examination.

8.5 MRI scans

Prior to the first functional MRI scan, an anatomical MRI scan will be performed. These anatomical scans will be reviewed by a qualified neuroradiologist and if any abnormalities are detected, the patient's GP will be informed, with their consent. They will be withdrawn from the study, in the case of abnormalities that would affect the study.

9. SAFETY MONITORING AND RISK MANAGEMENT

9.1. Safety Events and Reporting

During the study:

Any potential adverse events of the study will be reviewed regularly by the Chief Investigator, [name], and the other investigators. The safety of the subjects is of the highest importance throughout the study. An internal audit will be completed at the end of the study. Study progress and safety will be regularly reviewed in fortnightly meetings. A formal monitoring committee is not deemed necessary as the MC4R agonist (BMT) has been administered safely previously. If any subjects come to harm as a result of taking part in this research study the study will be terminated.

Adverse Events:

Adverse Event (AE): any untoward medical occurrence in a patient or clinical study subject.

Serious Adverse Event (SAE): any untoward and unexpected medical occurrence or effect that:

- Results in death
- Is life-threatening – refers to an event in which the subject was at risk of death at the time of the event; it does not refer to an event which hypothetically might have caused death if it were more severe
- Requires hospitalisation, or prolongation of existing inpatients' hospitalisation
- Results in persistent or significant disability or incapacity
- Is a congenital anomaly or birth defect

Medical judgement will be exercised in deciding whether an AE is serious in other situations. Important AEs that are not immediately life-threatening or do not result in death or hospitalisation but may jeopardise the subject or may require intervention to prevent one of the other outcomes listed in the definition above, will also be considered serious.

Reporting Procedures:

All adverse events will be reported. Depending on the nature of the event the reporting procedures below will be followed. Any questions concerning adverse event reporting will be directed to [name] in the first instance.

Non serious AE's

All such events, whether expected or not, will be recorded.

Serious AE's

An SAE form will be completed and faxed to [name] within 24 hours. However, relapse and death due to unrelated pre-existing conditions, and hospitalisations for elective treatment of a pre-existing condition do not need reporting as SAEs.

All SAEs should be reported to the local REC committee where in the opinion of the Chief Investigator, [name], the event was:

- 'related', i.e. resulted from the administration of any of the research procedures; and
- 'unexpected', i.e. an event that is not listed in the protocol as an expected occurrence

Reports of related and unexpected SAEs will be submitted within 15 days of the Chief Investigator, [name], becoming aware of the event, using the National Research Ethics Service (NRES) SAE form for non-IMP studies.

Local investigators will report any SAEs as required by their Local Research Ethics Committee, Sponsor and/or Research & Development Office.

All AE's/SAE's must be reported during the study, regardless of relationship to study intervention or clinical significance.

